^a The physical exam will be repeated at Visit 2 only if findings at previous visit are abnormal and clinically significant.

^b To be performed prior to dosing.

^d Obtain only for females of child-bearing potential.

^e Pre-dose sputum specimens (2 separate specimens) will be collected from each patient for central analysis (one each for microbiology [REDACTED] [REDACTED]). If a patient is unable to expectorate, one induced sputum specimen will be taken at baseline. For all post-baseline visits, a deep-throat cough swab can be collected from non-sputum producing patients for microbiology.

^f All subjects will have post-dose serum specimens collected during specified time windows. The time interval is measured from the completion of study drug administration. There must be a minimum of one hour difference between consecutive sampling points. Samples may be obtained from a peripheral site by phlebotomy or through a temporary i.v. site, but not through an existing central access or catheter. A patient who discontinues early and is on study medication will be asked to provide an extra serum specimen at the treatment discontinuation visit.

^g All patients will have post-dose sputum specimens collected for PK testing during specified time windows. The time interval is measured from the completion of study drug administration. In patients who are not able to spontaneously produce sputum, one specimen of induced sputum post-dose per specified interval will be collected. No induced sputum sample for PK will be collected at baseline in patients who had induced sputum pre-dose for microbiology assessments. A patient who discontinues early and is on study medication will be asked to provide an extra sputum specimen at the treatment discontinuation visit.

^h Subjects in the serum PK sub-study will have a pre-dose serum specimen collected prior to administration of study drug. A patient who discontinues early and is on study medication will be asked to provide a pre-dose serum specimen at the treatment discontinuation visit.

ⁱ Audiological assessments will be conducted at selected study sites or in patients with oto-toxic events. Auditory acuity will be measured at frequencies from 250 to 8000Hz using a standard dual-channel audiometer. Audiology can be performed within 3 days of the assigned visit.

^j If audiology is normal up to and including the end of the treatment epoch (Visit 106), audiological examination is not needed at Visits 201 and 202.

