6.5.7 Audiology

The patient should be questioned at each visit about the occurrence of any hearing abnormalities. If any such change is suspected by the patient, the investigator should have the case assessed and followed up by an audiologist, regardless of whether or not the site participates in the audiology sub-study. Audiological assessments will be conducted at selected study sites at Visits 2, 103, 104, 105, 106 (or discontinuation visit) and also at follow-up visits 201 and 202, as relevant. For patients whose audiology is normal up to and including the end of the treatment epoch (Visit 106), there is no need for additional audiology at Visits 201 and 202. If the audiology is abnormal at any visit, it should be repeated at all following visits including the end of study visit.

Patients will have auditory acuity measured using a standard dual-channel audiometer at frequencies from 250 Hz to 8 kHz. Measurements of interoctaves are not necessary. An audiogram (pure-tone air conduction) and tympanogram will be performed by an audiologist. Bone conduction will be performed if the air conduction shows a decrease of 20 dB from the patient's pre-dose measurements in either ear. Novartis and the investigator must be notified within 5 working days if a 20 dB drop versus as compared to the most recent pre-dose value (either screening or baseline) is noted in either ear. In this case, the patient will be withdrawn from treatment and monitored until auditory acuity values return to baseline or until the follow-up visit, whichever occurs first. Only at the baseline visit (Visit 2), the audiology assessment must be performed prior to dosing. At the following visits, audiology can be performed within 3 days before or after the assigned visit.

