9.5.2 Safety variables

All safety analyses will be performed using the safety population, and will be presented by treatment groups. Baseline for safety analyses is defined as the last measurement prior to the first dose of study medication in the study.

Appropriate summary statistics will be provided for laboratory test results, audiology, bronchial hyperreactivity and vital signs.

AEs will be deemed treatment-emergent if the onset date is on or after the date of first study drug and until study completion. Treatment emergent AEs will be summarized by MedDRA primary SOC and preferred term for each cycle and overall. The actual MedDRA version in effect at the time of the clinical study report will be used for coding AEs.

Audiology testing will be performed at selected centers and in patients with hearing events. Audiology function data will be analyzed via summary statistics by treatment and visit.

Clinical laboratory parameters will be summarized using means and mean changes from baseline to each post-baseline visit by treatment group. Shift-from-baseline summaries (shift tables) will be presented for the last available measurement (Termination Visit).

Vital sign parameters will be summarized using means and mean changes from baseline by treatment group and visit.

Analysis of post-inhalation events will be conducted for the two types of events (post-inhalation clinical events/post-inhalation adverse events). The number of patients with post-inhalation events will be summarized by treatment. In addition, the number of these events and the event rate adjusted for exposure will be displayed by treatment.

Post-inhalation events occurring at a site visit within 5 minutes (yes/no), post-inhalation events that are ongoing at completion of the site visit (yes/no) and for which an action taken to reduce the event (yes/no), the time-point of an event and the time of onset (≤ 30 sec, >30 sec-1min, >1 -2min, >2 -5min, >5 min) will be summarized with the number and percentage overall and for each cycle. Descriptive statistics including mean, standard deviation, minimum, median and maximum will be provided for the duration of the event in seconds.

[figure not shown]

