1.2.2 Secondary objectives

- To assess the effect of different doses of TIP administered o.d. and one b.i.d. dose and different regimens (TIP and TIP/placebo cyclical) on the frequency, rate (by patient months), severity and time to onset of pulmonary exacerbations at the end of the treatment epoch and over the entire study, each compared to placebo.
- To assess the efficacy profile of different doses of TIP administered o.d. and one b.i.d. dose and different regimens (TIP and TIP/placebo cyclical), as measured by the time to first use, proportion of patients requiring anti-pseudomonal antibiotics (overall, oral, parenteral) and the duration of treatment, each compared to placebo.

[figure not shown]
- To assess the time to first hospitalization, proportion of patients requiring hospitalization and the duration of hospitalization due to serious respiratory-related AEs (other than those regularly scheduled hospitalization that were planned prior to study start).
- To assess the pharmacokinetic concentrations of tobramycin in serum and in sputum from different doses of TIP administered o.d. and one b.i.d. dose and different regimens (TIP and TIP/placebo cyclical).
- To assess the antimicrobial efficacy of TIP over the entire study duration, as measured by the absolute change in *P. aeruginosa* -CFUs in sputum from baseline to each post-baseline treatment visit and during the follow-up visits.
- To evaluate the safety profile of TIP in terms of clinical laboratory results.
- To evaluate the safety profile of TIP in terms of audiology findings throughout the treatment epoch (subgroup of all patients that are in enrolled at sites that are adequately equipped and trained to perform audiologic assessments).
- To evaluate the safety profile of TIP in terms of acute change in forced expiratory volume at 1 second (FEV₁) % predicted values from pre-dose to 30±15 minutes after completion of study drug administration at the clinical site at visits during the treatment epoch.
- To evaluate the impact of treatment with TIP on the Respiratory Symptom Scale Quality of Life Questionnaire for Bronchiectasis (QOL-B) by measuring change from baseline to all post-baseline visits.

[figure not shown]
Table 1-1 Primary and secondary objectives and related endpoints

Objective	Endpoint	Statistical Analysis
Primary		

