2.2 Analysis sets

Safety Set (SAF): The safety set will be used for all safety analyses, which is defined as patients who received at least 1 dose of study drug. Patients will be analyzed according to the actual treatment received.

For the purposes of tables and listings a further 3 populations are defined:

- All enrolled patients (ENR)
- Screening failure patients
- Randomized population (RAN: all randomized patients)

Full Analysis Set (FAS): The full analysis set (FAS) will include all randomized patients who received at least 1 dose of study drug. Following the intent-to-treat principle, patients will be analyzed according to the treatment they are assigned to at randomization, which may be different from the actual treatment received. Patients who are mistakenly randomized or who have not taken double blind study drug will be excluded from the FAS. This is the primary analysis set for all efficacy analyses.

Per-Protocol Set (PPS): The per-protocol set (PPS) will include all patients in the FAS without any major protocol deviations.

Criteria for determining protocol deviations will be defined and documented in the protocol deviations section of the data validation specifications. Potential protocol deviators will be identified and reviewed to determine whether they will be excluded from the PPS population. This will take place in a blinded data review meeting prior to database lock. All protocol deviations will be agreed and documented prior to unblinding the study. The PPS will be used for the supportive analysis of the primary efficacy variable.

Pharmacokinetic Analysis Set (PKAS): The pharmacokinetic analysis set (PKAS) will include all patients who are administered TIP, and for whom results of plasma concentrations are obtained for at least one sampling point during the study.

Pharmacokinetic Sub-study Analysis Set (PKSSAS): The pharmacokinetic sub-study analysis set (PKSSAS) will include all patients enrolled in the pharmacokinetic sub-study

who are administered TIP, and for whom results of plasma concentrations are obtained for at least one sampling point during the study.

Audiology Population (AUD): The audiology population is defined as all patients in the safety set with at least one audiology test performed.

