2.7.4 Other safety data

2.7.4.1 Audiology testing

Audiology testing will be conducted at selected sites at Visit 2 (prior to dosing), Visit 102 (Day 8), Visit 103 (Day 29), Visit 104 (Day 57), Visit 105 (Day 85), Visit 106 or TD (Day 113), Follow-up Visit 201 (Day 141) and Follow-up Visit 202 or PSD (Day 169). Certain patient sub-groups are required to have audiology testing during the screening period.

The results of audiology testing will be summarized at each visit by the number and percentage of patients. Patients with the following decreases in consecutive frequencies will be presented for audiology safety: any frequencies decreased, 2 consecutive frequencies decreased, ≥ 10 dB decrease in ≥ 3 consecutive frequencies, ≥ 15 dB decrease in ≥ 2 consecutive frequencies, ≥ 20 dB decrease in at least 1 frequency. Events can be observed in either ear.

Results of the bone conduction test will be summarized with the number of patients who performed the test; the number and percentage of conductive, neurosensory and mixed hearing loss in left, right or both ears will also be given.

Summaries will be based on the AUD.

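### The audiology set is wider than the endpoint it serves, and percentages at Visits 201 and 202 are taken among patients retested because their audiology was abnormal

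*SAP*

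**What the plan says.** **Who the endpoint covers.** The secondary objective in SAP 1.2.2 names the "subgroup of all patients that are in enrolled at sites that are adequately equipped and trained to perform audiologic assessments" and, as in Protocol 2.2, concerns the treatment epoch. SAP Table 1-1 likewise restricts the audiology endpoint to selected centers.

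**Who is in the analysis set.** SAP 2.2: "The audiology population is defined as all patients in the safety set with at least one audiology test performed". There is no condition on site, on the reason for the test, or on having both a pre-dose and a post-dose result. SAP 2.7.4.1 bases the audiology summaries on this set.

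**Who is tested.** Protocol 9.5.2: "Audiology testing will be performed at selected centers and in patients with hearing events". Under Protocol 6.5.7, a suspected hearing change leads to an audiologist's assessment "regardless of whether or not the site participates in the audiology sub-study". Patients with primary ciliary dyskinesia or past significant hearing loss also have screening audiometry (Protocol 4.2 and Table 6-1).

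**Follow-up testing.** For patients with normal audiology through Visit 106, Protocol 6.5.7 says "there is no need for additional audiology at Visits 201 and 202". An abnormal result at any visit is followed by repeat tests at all later visits.

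**What is tabulated.** SAP 2.7.4.1, whose visit list includes 201 and 202: "The results of audiology testing will be summarized at each visit by the number and percentage of patients". The categories are decreases of stated size. SAP 2.1 bases percentages of categorical data on non-missing values.

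**The concern.** Two separate problems arise.

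First, the set combines patients tested on a schedule with patients tested because they noticed a problem, and with patients who have no post-dose test. The resulting percentage does not estimate the rate in the population that the objective names, and it depends partly on who complained.

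Second, whether a patient is retested at Visits 201 and 202 depends on the outcome being measured. Unaffected patients leave the denominator and affected patients stay in it.

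Ototoxicity is an adverse event of special interest, and the arms are small. With 107 randomized at 1:1:1 and then 2:2:1, each active arm has about 107 × 1/3 × 2/5 = 14 patients and each placebo arm about 107 × 1/3 × 1/5 = 7. If 30% to 70% are at audiology sites (assumed), about 4 to 10 per active arm and 2 to 5 per placebo arm are tested on schedule. One added or dropped patient then moves a percentage visibly: 0/6 becomes 1/7, or 14%.

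**Working it through.** The documents give no number of audiology sites, number tested or expected rate, so there is no figure of the plan's own to reproduce. The checks below concern direction and rough size. All rates and shares are assumptions.

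**1. Visits 201 and 202.** Let *a* be the share of systematically tested patients who are retested, and *r* the share of those who show a decrease. Assume that patients not retested stay normal.

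- Percentage among patients tested: *r*
- Percentage among all systematically tested patients: *a* × *r*
- Ratio: *r* / (*a* × *r*) = 1/*a*

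| Share retested (*a*) | Among tested, *r* = 50% | Among all systematically tested | Ratio |
|---|---|---|---|
| 10% | 50% | 5% | 10 |
| 20% | 50% | 10% | 5 |
| 30% | 50% | 15% | 3.3 |
| 50% | 50% | 25% | 2 |

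The ratio does not depend on *r*. If a share *f* of patients not retested also have a decrease, it falls to *r* / (*a* × *r* + (1 − *a*) × *f*), which still exceeds 1 whenever *f* is below *r*.

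**2. Treatment visits.** Let *s* be the share of patients at audiology sites, *p* the true rate of decrease, and *q1* and *q0* the chance of a triggered test elsewhere with and without a true decrease. The triggered share is T = (1 − *s*) × (*p* × *q1* + (1 − *p*) × *q0*).

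- *Triggered patients have a pre-dose audiogram:* rate = [*s* × *p* + (1 − *s*) × *p* × *q1*] / (*s* + T). With *s* = 0.3, *p* = 0.05, *q1* = 0.5 and *q0* = 0.02, this is (0.0150 + 0.0175) / (0.3 + 0.0308) = 9.8%, against a true 5%. With *q1* = *q0* = 0.3, it is 0.0255 / 0.51 = 5.0%, so there is no bias.
- *No pre-dose audiogram, non-missing denominator:* a decrease cannot be scored and the patient drops out. The rate stays at 5.0%.
- *No pre-dose audiogram, whole audiology set as denominator:* rate = *s* × *p* / (*s* + T). With *s* = 0.3, *p* = 0.05 and *q1* = *q0* = 0.3, it is 0.015 / 0.51 = 2.9%, so the rate is diluted.

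Across *s* = 0.3 to 0.7, *q1* = 0.3 to 0.5 and *q0* = 0.02 to 0.30, a true 5% reads as anything from 2.9% to 9.8%. Patients with only a screening or baseline audiogram can only dilute.

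**3. A pull in the other direction.** Under Protocol 5.6.2, a qualifying 20 dB drop ends study treatment, and the patient has a discontinuation visit and then enters follow-up. Suppose 16 patients are tested and 2 have such a drop at Visit 103. Visit 105 can then show 0/14, while the cumulative figure is 2/16 = 12.5%.

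**4. Visit lists.** SAP 2.7.4.1 includes Visit 102 (Day 8). Protocol 6.5.7 goes from Visit 2 to Visit 103. If the protocol list was followed, Day 8 results would come mainly from unscheduled tests.

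**The case against.** The defence has several sound points. Broad inclusion follows Protocol 9.5.2, which itself plans testing both at selected centers and in patients with hearing events. Safety analysis is descriptive. Ototoxicity events are also summarized over the full safety set, so audiology is not the only view of hearing risk. Listings show every test. Complaints arise under within-cohort blinding, so the trigger should act alike on active and placebo within a cohort. By-visit tables generally use nominal visits (SAP 2.1.1), so a triggered assessment elsewhere may not enter them at all. These points limit the consequence. They do not align the set with the endpoint in Table 1-1, and they do not correct the follow-up percentages.

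Two stronger readings are tempting, and the documents support neither.

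- *Hearing-loss percentages are inflated throughout.* A reader might add 5 to 10 triggered patients, 80% of them positive, to 32 to 54 scheduled patients with a 10% rate, and get about 16% to 27%. But a patient without a pre-dose audiogram, a case that Protocol 5.6.2 foresees, cannot be scored as a decrease. The upper end also contradicts its own inputs: the other 53 to 75 patients would yield only 5.3 to 7.5 cases at 10%, while ten triggered patients at 80% require 8.
- *Follow-up percentages must approach 100%.* Retesting depends on abnormal audiology, whereas the table counts decreases. A patient with a stable abnormal baseline is retested without showing a decrease, and some patients recover. The protocol also says only that testing normal patients is unnecessary; it does not bar it.

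**Conclusion.** The point holds in two parts of different strength.

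The mismatch between the audiology set and the endpoint population is plain from the text. Its effect on treatment-visit percentages is of uncertain direction, because it depends on whether triggered patients have a pre-dose audiogram, which denominator is used, and how many patients leave treatment after a drop.

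The follow-up overstatement follows from the documents' own rules if testing is largely confined to patients who need it and the non-missing denominator applies. Its size is about 1/(share retested), illustratively 2 to 10 times for 50% to 10% retested. This is measured against all systematically tested patients and assumes that those not retested stay normal. The true share is not given.

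**What to change.** - **Main table.** Base it on safety-set patients at selected audiology sites with a pre-dose and at least one scheduled post-dose audiogram. State the denominator at each visit.
- **Triggered tests.** Show complaint-triggered assessments separately as a count by arm and a listing, marking whether a pre-dose value exists, so that symptomatic patients stay visible.
- **Visits 201 and 202.** Give counts only, or persistence and recovery among patients previously abnormal, instead of a percentage of those tested. This stays within the as-observed rule and assumes nothing about untested patients.
- **Optional.** Add the worst on-treatment change per patient, which is not affected by patients leaving later treatment visits.
- **Visit 102.** Reconcile SAP 2.7.4.1 with Protocol 6.5.7.

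The cost is a revised definition in SAP 2.2, changes to the audiology table layout and footnotes, and slightly fewer patients in the main table. No new data are needed.

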2.2.1 Subgroups of interest

Primary endpoint analysis will be repeated in the subgroup of patients with/without macrolide treatment at baseline, only if clinical meaningful difference was observed between the pooled active doses vs placebo.

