5.3 Treatment assignment and randomization

At Visit 101 (see [Table 6-1](#)), all eligible patients/subjects will be randomized via Novartis Interactive Response Technology (NIRT) to one of the treatment arms with the randomization stratum (use of macrolides as part of their standard of care therapy). The investigator or his/her delegate will contact the NIRT after confirming that the patient fulfills all the inclusion/exclusion criteria. The NIRT will assign a randomization number to the patient, which will be used to link the patient to a treatment arm and will specify a unique medication number for the first package of investigational treatment to be dispensed to the patient. The randomization number will not be communicated to the caller.

The randomization numbers will be generated using the following procedure to ensure that treatment assignment is unbiased and concealed from patients and investigator staff. A patient randomization list will be produced by the Novartis IRT (NIRT) provider using a validated system that automates the random assignment of patient numbers to randomization numbers. These randomization numbers are linked to the different treatment arms, which in turn are linked to medication numbers. A separate medication list will be produced by or under the responsibility of Novartis Drug Supply Management using a validated system that automates the random assignment of medication numbers to packs containing the investigational drug(s).

Randomization by cohort and treatment arm will be stratified by use of macrolides.

The randomization scheme for patients/subjects will be reviewed and approved by a member of the Randomization Group.

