DMC	Data Monitoring Committee
DSPC	1, 2-distearoyl-sn-glycero-3-phosphocholine
eGFR	estimated Glomerular Filtration Rate
ENR	Enrolled Set
FAS	Full Analysis Set
FEF ₂₅₋₇₅	Forced Expiratory Flow at 25-75%
FEV ₁	Forced Expiratory Volume at 1 Second
FVC	Forced Vital Capacity
eCRF	electronic Case Report Form
ISC	Independent Study Coordinators
IRT	Interactive Response Technology
MedDRA	Medical Dictionary for Drug Regulatory Affairs
MIC	Minimum Inhibitory Concentration
o.d.	once a day
PCR	Protein-creatinine ratio
	
	
PK	Pharmacokinetics
PKAS	Pharmacokinetic Analysis Set
PKSSAS	Pharmacokinetic Sub-Study Analysis Set
PPS	Per-Protocol Set
PRO	Patient Reported Outcomes
PSD	Premature Subject/Patient Discontinuation
PT	Preferred Term
QoL	Quality of Life
QOL-B	Quality of Life Questionnaire for Bronchiectasis
RAN	Randomized population
SAF	Safety Set
SAP	Statistical Analysis Plan
SOC	System Organ Class

█
TBL

█
Total Bilirubin

TD

Study Treatment Discontinuation

TIP

Tobramycin inhalation powder

TFLs

Tables, Figures, Listings

ULN

Upper Limit of Normal

WHO

World Health Organization

1 Introduction

This statistical analysis plan (SAP) is based on the amended protocol version 02 dated 09th February 2018, and the business decision to close the trial earlier than planned (but not due to safety or efficacy reasons) by the Novartis. Recruitment has been stopped on 02nd October 2018 with 107 patients randomized as against 180 patients initially planned. With this premature closure and reduced sample size, the inferential analysis, regardless if it's pre-defined, can be considered as exploratory, the results obtained should be interpreted with the caution. The plan provides a technical and detailed elaboration of the statistical analyses of the efficacy, safety and tolerability of different doses of tobramycin inhalation powder (TIP) in patients with Non-Cystic Fibrosis Bronchiectasis and pulmonary *P. aeruginosa* infection. The specifications for tables, figures, and listings (TFLs) will be included in a separate document.

A clinical study report (CSR) will be written based on the results of the statistical analyses planned within this SAP. Results will also be used for the various publications.

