2.5.2 Statistical hypothesis, model, and method of analysis

The comparisons of 3 doses of active treatment (TIP 3 capsules OD, 5 capsules OD, and 4 capsules BID) versus pooled placebo will be evaluated by testing the following null hypothesis (H₀) versus the alternative hypothesis (H_a):

H₀: TIP treatment arm is equal to pooled placebo group in bacterial load in sputum at Day 29

H_a: TIP treatment arm is not equal to pooled placebo group in bacterial load in sputum at Day 29

The primary efficacy endpoint will be analyzed using the analysis of covariance (ANCOVA) model. The model will contain treatment, baseline CFU (in log₁₀ unit), and baseline macrolide use (yes/no). The adjusted means will be displayed together with the associated standard error and 2-sided 95% CI. Pairwise comparisons of TIP dosing groups will be conducted versus placebo. To control the family-wise type-I error rate (3 dose levels vs. placebo) at the 2-sided 5% significance level, the step-wise Dunnett procedure will be used.

For the primary efficacy analysis, patients from treatment arms TIP and TIP/placebo cyclical regimen will be pooled for each cohort. This is possible because all patients within the same cohort on the TIP treatment arms (cyclical or continuous) are receiving the same treatment during the first 28 days. Placebo patients will be pooled across the 3 cohorts, as the number of placebo capsules is not expected to influence the change in *P. aeruginosa* bacterial counts.

The estimated adjusted treatment difference (TIP – placebo) will be displayed along with the associated standard error, 2-sided 95% CI, and p-value (2-sided).

The estimated treatment difference and CI will be displayed in forest plot for the treatment arms TIP and TIP/placebo cyclical regimen pooled for each cohort vs pooled placebo across 3 cohorts.

For other efficacy analyses up to and including Day 29, patients from treatment arms TIP and TIP/placebo cyclical regimen will be pooled for each cohort; placebo patients will be pooled across the 3 cohorts.

If no *P. aeruginosa* isolated (NPAI) are detected, i.e, no growth detected, at a given visit where the laboratory sample was available at that visit, the value will be imputed as 99 based on the lower limit of detection (dilution factor is currently 1/100). Log 10(99) will be used in the analysis.

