2.12 Interim analysis

No interim analysis of efficacy is planned for this study.

The final analysis will be performed after the database is locked, the treatment assignments are unblinded using the actual randomization, and the database released.

An independent DMC is set-up to review safety data and provide the Sponsor with guidance on safety issues. SAE listings generated from the Novartis safety database, ARGUS, will be reviewed monthly by the DMC. The DMC will also perform a pre-planned review of AE and additional pre-defined safety data when approximately 50% of patients have completed the 28 days of treatment.

The membership of the DMC and the responsibilities of the DMC, [REDACTED] will be defined in a separate ‘DMC Charter’ document. The DMC Charter will include information about data flow, purpose and timings of DMC meetings, communication strategy, procedures for ensuring confidentiality, procedures to address conflicts of interest and statistical monitoring guidelines.

3 Sample size calculation

[figure not shown]
Sample size estimation was based on a difference of 2.0 log₁₀ CFU/g, with standard deviations of 2.0 log₁₀ CFU/g. The assumptions were based on conservative estimates from published results ([Konstan et al 2011a](#), [Konstan et al 2011b](#), [Barker et al 2000](#), and [Wilson et al 2013](#)).

As there are 3 primary comparisons between the 3 doses versus placebo, the Bonferroni multiplicity adjustment has been used (0.05/3) for sample size calculation. Using $\alpha=1.67\%$ (2-sided) and 90% power, the sample size estimation yielded $n = 36$ patients per treatment arm as valid for intent-to-treat (ITT) analyses. This takes into account an approximate 20%-discontinuation rate. For the primary efficacy analysis, patients from TIP continuous and TIP cyclical regimen within the same cohort will be pooled as they receive exactly the same treatment during the first 28 days. Placebo patients will be pooled across the 3 cohorts, as the number of placebo capsules is not expected to influence the change in *P. aeruginosa* bacterial counts. With the current study design, the power is 94% to detect a reduction of 2.0 log₁₀ CFU/g for each dose level versus placebo.

For calculation of sample size, NQuery Advisor version 7.0 module MTTO-1 was used.

4 Change to protocol specified analyses

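### The macrolide yes/no repeat of the primary analysis depends on an undefined observed difference, so reporting by the only randomisation stratum is result-dependent

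*SAP*

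**What the plan says.** Protocol 5.3 makes macrolide use the stratification factor: "Randomization by cohort and treatment arm will be stratified by use of macrolides". No other factor is named.

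SAP 2.2.1 plans one subgroup analysis of the primary endpoint: "Primary endpoint analysis will be repeated in the subgroup of patients with/without macrolide treatment at baseline". It is to be done "only if clinical meaningful difference was observed between the pooled active doses vs placebo". The visible text puts no value on a meaningful difference. A figure of 2.0 log10 CFU/g appears only as the sample-size assumption (Protocol 9.7, SAP 3).

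SAP 2.5.2 fits treatment, baseline log10 CFU and macrolide use as main effects, with no treatment-by-macrolide term. Its comparisons are by dose: "Pairwise comparisons of TIP dosing groups will be conducted versus placebo". SAP 2.6.3 adds six single-arm comparisons, and for selected endpoints it compares pooled continuous and pooled cyclical regimens, separately, with placebo. Neither section plans all active doses together against placebo.

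SAP 1 records that recruitment stopped at 107 of 180 patients and that "the inferential analysis, regardless if it's pre-defined, can be considered as exploratory".

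**The concern.** The condition uses an observed result, and SAP 2.12 places the final analysis after unblinding. Someone must therefore decide, with the data in view and no written rule, whether the difference is large enough for the stratum results to be produced.

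Two things follow. If the analysis is run only after a large observed difference, the stratum estimates that get reported are selected upwards. And the condition works against its purpose: when the drug acts mainly in one stratum, the pooled difference is diluted, so the table that would show this becomes less likely to be made. No other analysis in the visible documents fills the gap, because macrolide use otherwise enters the primary analysis only as a main effect. Protocol 1.2 says the data will guide dose selection for later studies, and whether background macrolide changes the effect bears on that.

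**Working it through.** **Inputs.** From the documents: SD 2.0 and difference 2.0 log10 CFU/g, 20% loss, alpha 0.05/3 two-sided (SAP 3); 2:2:1 allocation, so active to placebo 4:1 (SAP 1.1); 107 randomised (SAP 1). Assumed, because the documents give neither: a trigger of 1.0 to 2.0 log10, and a macrolide share of 20 to 50%. I also assume that 4:1 holds among evaluable patients. Reductions are written as positive numbers, and normal approximations are used from step 2 on.

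**1. The plan's own figures.** The t-based sample size is 29 per group, and 29/0.8 = 36.25 against the stated 36. With 36 placebo and 48 patients per dose, 20% loss leaves 28.8 and 38.4. Noncentral-t power is 94.2% against the stated 94%. The inputs are being read as the plan uses them.

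**2. Precision of the pooled difference at 107 patients.** Evaluable: 107 × 0.8 = 85.6, split 68.5 active and 17.1 placebo. SE = 2 × sqrt(1/68.5 + 1/17.1) = 0.54. Without loss it is 85.6 and 21.4, SE 0.48.

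**3. Selection effect on the pooled estimate.** For true difference D and trigger T, let a = (T − D)/SE. The chance that the analysis is run is 1 − Φ(a). The mean estimate given that it is run is D + SE × φ(a)/(1 − Φ(a)). With SE 0.54:

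| Trigger T | D = 0.5 | D = 1.0 | D = 2.0 |
|---|---|---|---|
| 1.0 | run 18%, +0.79 | run 50%, +0.43 | run 97%, +0.04 |
| 1.5 | run 3%, +1.21 | run 18%, +0.79 | run 82%, +0.17 |
| 2.0 | run 0.3%, +1.66 | run 3%, +1.21 | run 50%, +0.43 |

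The second figure in each cell is the excess over D.

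**4. Carry-over to the strata.** Take the pooled estimate as the precision-weighted mean of the two stratum estimates, with weights w = V(pooled)/V(stratum). Then Cov(stratum, pooled) = w × V(stratum) = V(pooled). The regression of each stratum estimate on the pooled one has slope 1, so each stratum inherits the same absolute shift. This holds for the pooled-active contrast within a stratum; it was not computed for each dose separately.

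**5. Dilution.** Suppose the true reduction is 2.0 without macrolides and 0 with them. At macrolide share m the pooled difference is 2(1 − m). Chance that the analysis is run, SE 0.54:

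| Trigger T | m = 20% (pooled 1.6) | m = 35% (pooled 1.3) | m = 50% (pooled 1.0) | Same 2.0 effect in both strata |
|---|---|---|---|---|
| 1.0 | 87% | 71% | 50% | 97% |
| 1.5 | 57% | 36% | 18% | 82% |
| 2.0 | 23% | 10% | 3% | 50% |

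At every trigger the analysis is less likely to be run when the strata differ than when they agree. In a simulation of this pattern at m = 35% without loss, a nominally significant interaction was present but not analysed in 13%, 33% and 47% of trials at triggers 1.0, 1.5 and 2.0.

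**6. What an unconditional analysis could show.** The SE of the interaction is SE/sqrt(m(1 − m)): 0.54/0.40 = 1.35 at m = 20%, 1.13 at 35%, 1.08 at 50%. The 95% CI half-widths are about 2.6, 2.2 and 2.1 log10. Power for a 2.0 log10 difference between strata is 32%, 42% and 46% (38 to 54% without loss).

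**The case against.** Much of the opposing case stands.

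- **Direction.** A reader might infer that stratum results appear only after a favourable result. That is the natural sense of the clause, but the wording states no direction.
- **No safeguard is removed.** A reader might infer that the SAP withdraws a planned check on effect modification. Protocol 9 plans no macrolide subgroup and no interaction test; the only visible subgroup there is patients with three or more prior exacerbations (9.5.1.2). The SAP adds a conditional look. Even when it is run, it repeats the analysis within strata and gives no interaction estimate.
- **The figures depend on an assumed trigger.** With a trigger of 1.0 and the design effect of 2.0, the excess is 0.04, or 2%. The 0.43 figure needs a true difference equal to the trigger.
- **Sparse data.** In the macrolide stratum, 17.1 evaluable placebo patients become about 3 to 9 at shares of 20 to 50%. Holding back such a table after early closure is understandable.
- **Limited consequence.** All inference is already called exploratory, all data are listed (SAP 2.1.3), and the condition is stated openly.

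It could also be said that the clause means the dose groups of SAP 2.5.2, each pooled over regimen. All doses combined is the plainer reading. On the other reading the rule still lacks a threshold and does not say how many of the three differences must qualify.

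Sparsity is a reason for wide intervals and a pooled-active contrast, not for a trigger that depends on the result. Listings are not a stratum estimate. With inference already exploratory, there is no alpha for the condition to protect.

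**Conclusion.** The point holds as a minor one about result-dependent reporting. The only macrolide-stratum analysis of the primary endpoint hangs on an undefined observed difference in a contrast the plan does not otherwise make, and it tends not to be run when an effect confined to one stratum dilutes that difference.

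The bias cannot be sized from the documents. Under the stated assumptions (SD 2.0, 107 patients, 20% loss, trigger 1.0), the pooled estimate given that the analysis is run is too large by 0.43 log10 at a true difference of 1.0 and by 0.04 at 2.0. Stratum estimates shift by a similar absolute amount if the effect is the same in both strata. A higher trigger gives larger shifts.

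A reader might go further and conclude that the stratum results are materially biased or that the primary result is compromised. The documents do not support either. The dose-versus-placebo comparisons are reported whatever happens, and their alpha, power and sample size do not change.

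**What to change.** In SAP 2.2.1, delete the clause that makes the analysis conditional. Report, whatever the overall result and labelled exploratory, the Day 29 pooled-active versus pooled-placebo difference in each macrolide stratum and the treatment-by-macrolide interaction estimate, each with a 95% CI. Pooling the doses keeps the strata from being cut into groups too small to read.

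If the sponsor prefers to keep a condition, the minimum is to fix its contrast, threshold and direction before unblinding. That removes the discretion but not the selection.

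The cost is one deleted clause and one extra table. The estimates will be imprecise, since about 17 to 21 placebo patients are split between two strata, and the table should say so.
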